5.2. Exclusion Criteria

Participants are excluded from the study if any of the following criteria apply:

Medical Conditions:

1. Evidence or history of clinically significant hematological, renal, endocrine, pulmonary, gastrointestinal, cardiovascular, hepatic, psychiatric, neurological, or allergic disease (including drug allergies, but excluding untreated, asymptomatic, seasonal allergies at the time of dosing), as well as presence of lipid panel abnormalities (eg, hypercholesterolemia, hypertriglyceridemia).

- 2. Evidence of history of orthostatic hypotension or symptomatic bradycardia.
- 3. Any condition possibly affecting drug absorption (eg, gastrectomy, cholecystectomy).
- 4. History of phototoxicity or photosensitivity.
- 5. History of HIV infection, hepatitis B, or hepatitis C; positive testing for HIV, hepatitis B surface antigen (HBsAg), hepatitis B core antibody (HBcAb) or hepatitis C antibody (HCVAb). Hepatitis B vaccination is allowed. As an exception a positive HBsAb test due to hepatitis B vaccination is permissible.
- 6. Other medical or psychiatric condition including recent (within the past year), or active suicidal ideation/behavior, or laboratory abnormality, or other condition or situation related to the COVID-19 pandemic that may increase the risk of study participation or, in the investigator's judgment, make the participant inappropriate for the study.

Prior/Concomitant Therapy:

7. Use of prescription or nonprescription drugs and dietary and herbal supplements within 7 days or 5 half-lives (whichever is longer) prior to the first dose of study intervention. (Refer to Section 6.5 for additional details).

Prior/Concurrent Clinical Study Experience:

8. Previous administration with an investigational drug within 30 days (or as determined by the local requirement) or 5 half-lives preceding the first dose of study intervention used in this study (whichever is longer).

Diagnostic Assessments:

- 9. A positive urine drug test at screening or admission and confirmed by a single repeat test, if deemed necessary.
- Screening supine BP ≥140 mm Hg (systolic) or ≥90 mm Hg (diastolic), following at least 5 minutes of supine rest. If BP is ≥140 mm Hg (systolic) or ≥90 mm Hg (diastolic), the BP should be repeated 2 more times and the average of the 3 BP values should be used to determine the participant's eligibility.
- 11. Current findings or documented past history of blood pressure values <90 mmHg systolic or <50 mmHg diastolic.
- 12. 12-lead ECG that demonstrates clinically relevant abnormalities that may affect participant safety or interpretation of study results (eg, baseline QTc interval >450 msec, complete LBBB, signs of an acute or indeterminate-age myocardial infarction, ST-T interval changes suggestive of myocardial ischemia, second- or third-degree AV block, or serious bradyarrhythmias or tachyarrhythmias). If the

PFIZER CONFIDENTIAL

Page 29

baseline uncorrected QT interval is >450 msec, this interval should be rate-corrected using the Fridericia method and the resulting QTcF should be used for decision making and reporting. If QTc exceeds 450 msec, or QRS exceeds 120 msec, the ECG should be repeated 2 more times and the average of the 3 QTc or QRS values should be used to determine the participant's eligibility. Computer-interpreted ECGs should be overread by a physician experienced in reading ECGs before excluding participants.

- 13. Participants with ANY of the following abnormalities in clinical laboratory tests at screening, as assessed by the study-specific laboratory and confirmed by a single repeat test, if deemed necessary:
 - AST or ALT level $\geq 1.0 \times$ ULN;
 - Total bilirubin level ≥1.5 × ULN; participants with a history of Gilbert's syndrome may have direct bilirubin measured and would be eligible for this study provided the direct bilirubin level is ≤ULN;
 - Any lipid panel parameter (ie, total cholesterol, triglycerides, HDL, and/or LDL) ≥1.25× ULN.
- 14. A positive COVID-19 test.

Other Exclusions:

- 15. History of alcohol abuse or binge drinking and/or any other illicit drug use or dependence within 6 months of Screening. Binge drinking is defined as a pattern of 5 (male) and 4 (female) or more alcoholic drinks in about 2 hours. As a general rule, alcohol intake should not exceed 14 units per week (1 unit = 8 ounces (240 mL) beer, 1 ounce (30 mL) of 40% spirit or 3 ounces (90 mL) of wine).
- 16. Use of tobacco or nicotine containing products in excess of the equivalent of 5 cigarettes/day or 2 chews of tobacco/day.
- 17. Blood donation (excluding plasma donations) of approximately 1 pint (500 mL) or more within 60 days prior to dosing.
- 18. History of sensitivity to heparin or heparin-induced thrombocytopenia.
- 19. Unwilling or unable to comply with the criteria in the Lifestyle Considerations section of this protocol.
- 20. Investigator site staff or Pfizer employees directly involved in the conduct of the study, site staff otherwise supervised by the investigator, and their respective family members.

5.3. Lifestyle Considerations

The following guidelines are provided:

5.3.1. Meals and Dietary Restrictions

- Participants must abstain from all food and drink (except water) at least 12 hours prior to any safety laboratory evaluations and 10 hours prior to the collection of the predose PK sample.
- Water is permitted until 1 hour prior to study intervention administration. Water may be consumed without restriction beginning 1 hour after dosing. Noncaffeinated drinks (except grapefruit or grapefruit-related citrus fruit juices—see below) may be consumed with meals and the evening snack.
- Lunch will be provided approximately 4 hours after dosing.
- Dinner will be provided approximately 9 to 10 hours after dosing.
- An evening snack may be permitted.
- Participants will refrain from consuming red wine, grapefruit, or grapefruit-related citrus fruits (eg, Seville oranges, pomelos, fruit juices) from 7 days prior to the first dose of study intervention until collection of the final PK blood sample.
- While participants are confined, their total daily nutritional composition should be approximately 55% carbohydrate, 30% fat, and 15% protein. The daily caloric intake per participant should not exceed approximately 3200 kcal.

5.3.2. Caffeine, Alcohol, and Tobacco

- Participants will abstain from caffeine-containing products for ≥24 hours prior to the start of dosing until collection of the final PK sample of each study period.
- Participants will abstain from alcohol for ≥24 hours prior (or as specified above for red wine) to admission to the CRU and continue abstaining from alcohol until collection of the final PK sample of each study period. Participants may undergo an alcohol breath test or blood alcohol test at the discretion of the investigator.
- Participants will abstain from the use of tobacco- or nicotine-containing products for ≥24 hours prior to dosing and during confinement in the CRU.

5.3.3. Activity

• Participants will abstain from strenuous exercise (eg, heavy lifting, weight training, calisthenics, aerobics) for at least 48 hours prior to each blood collection for clinical laboratory tests. Walking at a normal pace will be permitted.

- In order to standardize the conditions on PK sampling days, participants will be required to refrain from lying down (except when required for BP, pulse rate, and ECG measurements), eating, and drinking beverages other than water during the first 4 hours after dosing.
- Participants will be confined to the procedure room for the first 4 hours after dosing on Day 1 during continuous cardiac monitoring, except to use the bathroom. After this, if the equipment setup allows, participants may be ambulatory during the ECG monitoring period, but should not engage in strenuous activities. If equipment does not allow ambulation, appropriate accommodations will be made by the investigator site to facilitate continuous monitoring (eg, bedside urinals should be provided to accommodate participants' excretory needs).
- Participants will be advised to avoid direct sunlight exposure or any high intensity UV light exposure, from admission in Period 1 through the follow-up contact. In addition, participants will be instructed to apply sun cream/lotion with a sun protection factor (SPF) of ≥50, as appropriate.

5.3.4. Contraception

Contraception is only required for male study participants and is recommended for partners of male study participants who are WOCBP.

The investigator or his or her designee, in consultation with the participant, will confirm that the participant has selected an appropriate method of contraception for the individual participant and his or her partner(s) from the permitted list of contraception methods (see Appendix 4 Section 10.4.4) and will confirm that the participant has been instructed in its consistent and correct use. At time points indicated in the schedule of activities (SoA), the investigator or designee will inform the participant of the need to use highly effective contraception consistently and correctly and document the conversation and the participant's affirmation in the participant's chart (participants need to affirm their consistent and correct use of at least 1 of the selected methods of contraception). In addition, the investigator or designee will instruct the participant to call immediately if the selected contraception method is discontinued or if pregnancy is known or suspected in the participant or partner.

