5.1. Inclusion Criteria

Participants are eligible to be included in the study only if all of the following criteria apply:

Age and Sex:

- 1. Female participants of nonchildbearing potential and males must be 18 to 55 years of age, inclusive, at the time of signing the ICD.
 - Refer to Appendix 4 for reproductive criteria for male (Section 10.4.1) and female (Section 10.4.2) participants.

Type of Participant and Disease Characteristics:

- 2. Female participants of non-child bearing potential and male participants and who are overtly healthy as determined by medical evaluation including medical history, physical examination, neurological examination, laboratory tests, and cardiac monitoring.
- 3. Participants who are willing to avoid direct sunlight exposure or any high intensity ultraviolet light exposure from admission to the follow-up contact and to apply sunscreen/lotion with a high sun protection factor, as appropriate.
- 4. Participants who are willing and able to comply with all scheduled visits, treatment plan, laboratory tests, lifestyle considerations, and other study procedures.

Weight:

5. BMI of 17.5 to 30.5 kg/m²; and a total body weight >50 kg (110 lb).

Informed Consent:

6. Capable of giving signed informed consent as described in Appendix 1, which includes compliance with the requirements and restrictions listed in the ICD and in this protocol.

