10.4. Appendix 4: Contraceptive Guidance

10.4.1. Male Participant Reproductive Inclusion Criteria

Male participants are eligible to participate if they agree to the following requirements during the intervention period and for at least 28 days after the last dose of study intervention, which corresponds to the time needed to eliminate reproductive safety risk of the study intervention(s):

• Refrain from donating sperm.

PLUS either:

• Be abstinent from heterosexual intercourse with a female of childbearing potential as their preferred and usual lifestyle (abstinent on a long-term and persistent basis) and agree to remain abstinent.

OR

- Must agree to use a male condom when engaging in any activity that allows for passage of ejaculate to another person.
- In addition to male condom use, a highly effective method of contraception is recommended for WOCBP partners of male participants (refer to the list of highly effective methods below in Section 10.4.4).

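### The recurring contraception check in Protocol 5.3.4 tests the partner method list, not the male rule in 10.4.1, so it can record compliance for a non-abstinent man who uses no condom

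*Protocol*

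**What the plan says.** **The male rule.** Inclusion criterion 1 (Protocol 5.1) sends the reader to the appendix: "Refer to Appendix 4 for reproductive criteria for male (Section 10.4.1"). Section 10.4.1 applies "during the intervention period and for at least 28 days after the last dose of study intervention". It has two parts. The first is "Refrain from donating sperm". The second is a choice between long-term abstinence, as defined there, and a condom: "Must agree to use a male condom when engaging in any activity that allows for passage of ejaculate to another person". Beyond the condom, "a highly effective method of contraception is recommended for WOCBP partners of male participants".

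**The recurring check.** Section 5.3.4 opens by saying that contraception is required only of male participants and is recommended for their partners of childbearing potential. It then has the investigator confirm a method chosen "from the permitted list of contraception methods (see Appendix 4 Section 10.4.4"). At each time point in the Schedule of Activities, staff are to "inform the participant of the need to use highly effective contraception consistently and correctly". The pass condition is that "participants need to affirm their consistent and correct use of at least 1 of the selected methods of contraception". The section does not cite 10.4.1 and names neither the condom nor sperm donation. Footnote g of the Schedule of Activities names no method.

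**Two other places.** Section 4.2 makes a highly effective method the requirement for men and refers to Appendix 4. The lead-in to 10.4.4 presents its list as methods that partners of childbearing potential are to use. Sections 4.2, 5.3.4 and 10.4.1 and footnote g all say recommended on the partner side.

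**The concern.** A recurring check should test the rule that participants agreed to at entry. This one tests something else. Section 4.2 says that the measures expected of men are there to limit transfer of the drug to partners in semen. A partner's IUD or a vasectomy prevents conception but does not prevent that transfer. Within 10.4.1, the condom (or abstinence) serves that purpose, and the check as written does not ask about it.

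What is at stake is partner safety and the meaning of the source record. A chart could show an affirmation at every visit for a man who has been breaching 10.4.1 throughout. Site staff would also find three sections giving different accounts of what men and partners must do.

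**Working it through.** No calculation decides this point. It turns on comparing the two rules and running cases through them.

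| Item | 10.4.1 (binding on men) | 5.3.4 check |
|---|---|---|
| Sperm donation | Prohibited | Not asked |
| Male condom | Required unless abstinent | Not named; in 10.4.4 it is one of several add-on barriers for user-dependent methods |
| Abstinence | The alternative to the condom; must be the man's settled lifestyle | Item 8 of 10.4.4, defined by the period of risk |
| Highly effective method | Recommended for partners of childbearing potential, on top of the condom | What staff tell the man he needs |
| Pass condition | No donation, and abstinence or condom | At least one selected method |

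**Cases**

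1. *Vasectomized, not abstinent, no condom.* Item 5 of 10.4.4 lists vasectomy, subject to its own conditions (sole partner, sperm shown to be absent). He can truthfully affirm one selected method and passes. Section 10.4.1 has no exemption for vasectomy, so he is in breach.
2. *Partner has an IUD, implant or tubal occlusion; no condom.* These are items 2, 1 and 4. On the literal affirmation wording he passes, and he is in breach of 10.4.1.
3. *Partner uses a hormonal method together with a male condom.* He passes the check and meets the condom part of 10.4.1. No conflict.
4. *Abstinent as 10.4.1 defines it.* He meets that part of the rule. The condom gap does not touch him.
5. *Any man who donates sperm.* The check has no item that would bring this out.

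**How often the check is made.** The contraception row of the Schedule of Activities, for a man who completes everything (early termination not counted), gives:

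- screening 1 + 4 periods × 2 (Day -1 and 48 h) + follow-up visit 1 + follow-up contact 1 = 11;
- before the first dose: screening and Period 1 Day -1 = 2; after it: 11 − 2 = 9;
- of those 9, the four 48-hour checks look back only on time in the unit;
- the other 5 (Day -1 of Periods 2, 3 and 4, the follow-up visit, the follow-up contact) look back on time at home.

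**How long the rule applies at home.** Assume discharge at 48 hours and readmission one day before the next dose. An interval of W days between doses then leaves W − 3 days at home, and the 28 days after the last dose leave 28 − 2 = 26.

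- W = 7, the minimum: 3 × 4 + 26 = 38 days.
- W = 14, assumed: 3 × 11 + 26 = 59 days.

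The second value is plausible. About 14 weeks (98 days) of participation, less up to 28 days of screening and 28 to 35 of follow-up, leaves 35 to 42 days over three intervals, or about 12 to 14 days each. These figures say how long the rule runs outside the unit. They do not measure breach or exposure.

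**The case against.** The strongest reply is that nothing is missing. Criterion 1 points to 10.4.1 by number, and 10.4.1 states every term in full. Keeping a rule in one appendix is good practice. Read with its opening sentence, 5.3.4 asks the man for his own method and treats a partner's IUD as the recommended extra. The consent document and the site's source form, neither of which is available here, may state the condom and sperm-donation terms. Section 5.3.4 also asks for an immediate call if pregnancy is suspected, and 8.3.5.1 requires exposure during pregnancy to be reported within 24 hours.

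Much of this stands. The requirement exists, and the favourable reading narrows the gap. It does not close it: vasectomy is a man's own method and is on the list, so case 1 still passes while in breach, and sperm donation is still not asked about. The pregnancy provisions act only after the event.

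A reader might infer more than the text supports:

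- *That men are not bound to use condoms.* They are, through 10.4.1.
- *That the wording in 4.2 causes the failed check.* The check does not run from 4.2, which is design rationale and refers to Appendix 4. The conflict there is a separate inconsistency.
- *That abstinence is the only 10.4.4 entry compatible with 10.4.1.* A hormonal method with a male condom also meets the condom part. The text available shows one heading over all eight methods, so which of them count as user-dependent is partly inference.
- *That the check fails a man who uses only condoms.* The text is ambiguous. Section 10.4.4 names the male condom, though only as an add-on, and the affirmation itself does not say highly effective.
- *That the absent embryo-fetal studies are the stated reason for the male measures.* In 4.2 they explain why female participants must be of nonchildbearing potential. For men, 4.2 cites semen transfer and the lack of human reproductive safety data, and says that teratogenicity is not suspected from the pharmacology.

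**Conclusion.** The point holds in a limited form. The 5.3.4 check can record compliance for a non-abstinent man who uses no condom. The vasectomized man is the clear case; the man with a partner on a low-maintenance method is a case on the literal wording. The check never covers sperm donation. Separately, 4.2 and the 10.4.4 lead-in conflict with 10.4.1 over which measures are required and which are recommended.

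Severity is low. The number of men affected cannot be derived, because the documents give neither the sex split nor partner status. There is no effect on endpoints, analysis sets or PK. The conclusion concerns the protocol text and assumes that site staff run the check as 5.3.4 is written; a source form that already follows 10.4.1 would remove the practical gap but leave the inconsistency.

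**What to change.** 1. **5.3.4:** cite 10.4.1 as the male requirement. Replace the highly effective and one-selected-method wording so that, at each check after the first dose, the man affirms no sperm donation and either abstinence or male condom use, both as defined in 10.4.1. Describe partner methods from 10.4.4 as recommended. Adding a cross-reference alone would not be enough, because the one-method pass condition would remain.
2. **4.2:** replace the clause that makes a highly effective method mandatory for men with a reference to the 10.4.1 requirements.
3. **10.4.4 lead-in:** change *are to be used by* to *are recommended for*.

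The cost is wording in three protocol sections, and in the site's contraception-check form if that form follows 5.3.4. No visits, tests or participants are added. Recording the partner's method at every check is not needed to close the gap.

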5.4. Screen Failures

Screen failures are defined as participants who consent to participate in the clinical study but are not subsequently randomly assigned to study intervention/enrolled in the study. Screen failure data are collected and remain as source and are not reported to the clinical database.

Individuals who do not meet the criteria for participation in this study (screen failure) may not be rescreened.

6. STUDY INTERVENTION

Study intervention is defined as any investigational intervention(s), marketed product(s), placebo, medical device(s), or study procedure(s) intended to be administered to a study participant according to the study protocol.

For the purposes of this protocol, study intervention refers to all of the following:

- PF-07258669;
- Placebo for PF-07258669.

6.1. Study Intervention(s) Administered

PF-07258669 and placebo will be provided by Pfizer as bulk powders for extemporaneous preparation of oral solutions and suspensions at the CRU.

PF-07258669 and placebo will be presented to the participants in individual dosing containers.

6.1.1. Administration

Following an overnight fast of at least 10 hours, participants will receive study intervention at approximately 0800 hours (plus or minus 2 hours) without breakfast on Day 1.

Investigator site personnel will administer a single oral dose of study intervention on Day 1 of each period with ambient temperature water to a total volume of approximately 240 mL. Study intervention will be administered according to the EDR.

6.2. Preparation/Handling/Storage/Accountability

- 1. The investigator or designee must confirm appropriate temperature conditions have been maintained during transit for all study interventions received and any discrepancies are reported and resolved before use of the study intervention.
- 2. Only participants enrolled in the study may receive study intervention and only authorized site staff may supply or administer study intervention. All study interventions must be stored in a secure, environmentally controlled, and monitored (manual or automated recording) area in accordance with the labeled storage conditions with access limited to the investigator and authorized site staff. At a minimum, daily minimum and maximum temperatures for all site storage locations must be documented and available upon request. Data for nonworking days must indicate the minimum and maximum temperatures since previously documented for all site storage locations upon return to business.

- 3. Any excursions from the study intervention label storage conditions should be reported to Pfizer upon discovery along with any actions taken. The site should actively pursue options for returning the study intervention to the storage conditions described in the labeling, as soon as possible. Once an excursion is identified, the study intervention must be quarantined and not used until Pfizer provides permission to use the study intervention. Specific details regarding the definition of an excursion and information the site should report for each excursion will be provided to the site in the CRU site procedures.
- 4. Any storage conditions stated in the SRSD will be superseded by the storage conditions stated on the label.
- 5. Study interventions should be stored in their original containers.
- 6. See the EDR for storage conditions of the study intervention once prepared.
- 7. The investigator, institution, or the head of the medical institution (where applicable) is responsible for study intervention accountability, reconciliation, and record maintenance (ie, receipt, reconciliation, and final disposition records), such as the IPAL or sponsor-approved equivalent. All study interventions will be accounted for using a study intervention accountability form/record.
- 8. Further guidance and information for the final disposition of unused study interventions are provided in the CRU site procedures. All destruction must be adequately documented. If destruction is authorized to take place at the investigator site, the investigator must ensure that the materials are destroyed in compliance with applicable environmental regulations, institutional policy, and any special instructions provided by Pfizer.

Upon identification of a product complaint, notify the sponsor within 1 business day of discovery.

